### 7.3.3.2 Average daily severity score of mild to severe VMS

The daily VMS severity score is defined as  $(1xFmi + 2xFmo + 3xFse)/(Fmi + Fmo + Fse)$ , where Fmi, Fmo, and Fse are the daily frequencies of mild, moderate, and severe VMS, respectively. It will be rounded off the third decimal place and reported the value to the second decimal place.

The avarage daily VMS severity of mild to severe VMS at a time point (Week 12 (Baseline), 13, 14, ..., 64) is the average of the daily severity of available diary days in the corresponding 7-day window defined in Table 5.

A daily severity score of zero (0) is assigned if it is reported that no VMS occurred on that day. VMS data on the day of Week 64 visit is not used for the calculation of average daily VMS severity. If the count of available VMS data in a specific week is less than four (4), latest diaries in the previous window can be carried as needed to make 4 diaries available in this window. Then the average daily VMS severity in the week is calculated.

### 7.3.3.3 MENQOL scores deriving

The MENQOL is self-administered and consists of a total of 29 items in a Likert-scale format. Each item assesses the impact of one of four domains of menopausal symptoms, as experienced over the last month:

- vasomotor (items 1–3)
- psychosocial (items 4–10)
- physical (items 11–26)
- sexual (items 27–29)

Items pertaining to a specific symptom are rated as present or not present, and if present, how bothersome on a zero (not bothersome) to six (extremely bothersome) scale. Means are

computed for each subscale by dividing the sum of the domain's items by the number of items within that domain. Non-endorsement of an item is scored a "1" and endorsement a "2," plus the number of the particular rating, so that the possible score on any item ranges from one to eight. (Hilditch JR, et al. 1996) Total MENQOL score will be calculated as the average of each domain score.

## **8. STATISTICAL METHODOLOGY**

### **8.1 Study Subjects**

#### **8.1.1 Disposition of Subjects**

The number of subjects who enter study A02 will be summarized (Table 14.1.1)

Subject disposition will be summarized for subjects completion status and discontinue reasons in tables for each treatment group of MT-8554-A01, and overall.

The data listing for Subject disposition will be generated.

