4.1 Number of subjects

It is planned to enroll up to 364 subjects who have completed Study MT-8554-A01. The study will be finished when approximately 100 subjects complete a 52-week open-label treatment period and 30-day follow-up.

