4.6 Study completion criteria

The study will be completed by the Sponsor when approximately 100 subjects complete a 52-week open-label treatment period and 30-day follow-up. Further treatment of study drug will not be allowed. At the completion of the study all subjects will be required to have EOT visit assessments within the defined visit window. All subjects will be followed for 30 days for AEs, and unresolved AEs or SAEs will be followed up according to Section 8.10.

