5.1 Subject informed consent

Prior to performing any study procedures, the Investigator (or designated personnel) will ensure that the subject is given full and adequate oral and written information about the study and the subject must sign the informed consent form (ICF), as described in Section 11.2.1.

Based upon the results of Study MT-8554-A01, the dose is changed from 10 mg to 5 mg. The Investigator (or designated personnel) will ensure that the participating subject must provide reconsent to continue the study and the subject who reconsent to continue the study will receive MT-8554 5 mg.

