## **6. GENERAL CONSIDERATIONS**

### **6.1 Descriptive Statistics**

Continuous data will be summarized descriptively using the number of observations, mean, standard deviation (SD), median, minimum and maximum. Categorical data will be summarized using frequency counts and percentages. The denominator for the percentages will be the total number of subjects in the treatment group and analysis population being presented, unless otherwise specified.

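### If clearly more than 100 women would finish, closing the study at about 100 completers fixes the overall completion percentage near 100/N; the SAP gives women cut off by closure no status and plans no time-to-discontinuation estimate.

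*SAP*

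**What the plan says.** Protocol 4.1: "It is planned to enroll up to 364 subjects who have completed Study MT-8554-A01". Protocol 4.6: "The study will be completed by the Sponsor when approximately 100 subjects complete a 52-week open-label treatment period and 30-day follow-up". The same section adds: "Further treatment of study drug will not be allowed". It also requires end-of-treatment assessments of every subject when the study is completed. Protocol Table 1, footnote 4, asks for that visit from treatment completers and early withdrawals alike, so having the visit does not tell the two apart.

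Protocol 5.1, on the change of dose: "participating subject must provide reconsent to continue the study".

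The SAP repeats the enrolment ceiling in section 3.3 but does not mention the 100-completer rule. Section 8.1.1 states: "Subject disposition will be summarized for subjects completion status and discontinue reasons in tables for each treatment group of MT-8554-A01, and overall". It adds a listing. It does not define completion, list the reason categories, or say where a woman stopped by closure belongs. Protocol 4.5.2 lists the grounds for discontinuing a subject, and study closure is not among them. On percentages, SAP 6.1 states: "The denominator for the percentages will be the total number of subjects in the treatment group and analysis population being presented, unless otherwise specified". No time-to-discontinuation analysis appears in the SAP.

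**The concern.** Tolerability is part of the primary objective, and how many women stay on a drug for a year is one of the plainest descriptions of it. Here the study closes when a fixed number have completed. If that number is reached while others are still on treatment, the numerator of the completion percentage is set by the sponsor's rule and the denominator by enrolment. A well tolerated and a poorly tolerated drug could then give almost the same figure.

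The discontinuation percentage is affected too, though less. A woman cut off at month 6 stays in its denominator, but a stop she would have made at month 9 is never seen.

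With completion undefined, two programmers could also classify the cut-off women differently, and the table would change accordingly.

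**Working it through.** The plan states no completion percentage, dropout rate or power, so there is no figure of its own to reproduce.

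**Inputs from the documents.** About 100 completers of 52 weeks plus 30 days (Protocol 4.1, 4.6); enrolment up to 364 (Protocol 4.1); all subjects as denominator (SAP 6.1).

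**Assumptions, not in the documents.** N = 200 or 364 enrolled; uniform entry over 26, 52 or 78 weeks; exponential time to stopping, giving true 52-week retention R; closure when the 100th woman finishes 52 weeks plus 30 days.

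**Step 1. When the rule binds.** It binds when N × R is above 100, that is R > 100/N.
- N = 364: 100/364 = 27.5%
- N = 200: 100/200 = 50.0%

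When it binds, completion of treatment plus follow-up is 100/N: 27.5% at 364, 33.3% at 300, 40.0% at 250, 50.0% at 200.

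**Step 2. Simulation at N = 364, 1,000 runs per row.** Completion here means 52 weeks of treatment. It exceeds 100/N because some women have finished treatment but are still in follow-up at closure. The shortfall is true dropout (100 − R) minus the crude discontinuation percentage.

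| Accrual (weeks) | True retention % | Completed 52 weeks % | On treatment at closure % | Discontinued, crude % | Shortfall (points) |
|---|---|---|---|---|---|
| 26 | 40 | 34.0 | 6.2 | 59.8 | 60 − 59.8 = 0.2 |
| 26 | 70 | 39.0 | 32.1 | 28.8 | 30 − 28.8 = 1.2 |
| 26 | 90 | 42.4 | 48.3 | 9.4 | 10 − 9.4 = 0.6 |
| 52 | 40 | 30.8 | 10.3 | 59.0 | 60 − 59.0 = 1.0 |
| 52 | 70 | 33.2 | 40.5 | 26.3 | 30 − 26.3 = 3.7 |
| 52 | 90 | 34.9 | 57.0 | 8.1 | 10 − 8.1 = 1.9 |
| 78 | 40 | 29.7 | 12.6 | 57.8 | 60 − 57.8 = 2.2 |
| 78 | 70 | 31.3 | 45.2 | 23.5 | 30 − 23.5 = 6.5 |
| 78 | 90 | 32.5 | 60.5 | 7.0 | 10 − 7.0 = 3.0 |

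Retention more than doubles within each accrual period, yet completion rises by 42.4 − 34.0 = 8.4 points at most. Counting treatment plus follow-up, it is 27.5% in every row. The share on treatment at closure carries most of the difference.

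**Step 3. Smaller enrolment, N = 200.** At 40% retention the rule never bound and completion was 40%, equal to retention. With 52-week accrual, completion of treatment was 54.8%, 55.8%, 56.7% and 57.5% at retention of 60%, 70%, 80% and 90%. So completion tracks retention up to about 50% and then flattens.

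**Step 4. Kaplan-Meier.** In the same model, 1 minus the Kaplan-Meier estimate at 52 weeks, censored at closure or completion, recovered true discontinuation to within simulation error in every scenario.

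**The case against.** The strongest reply is that section 8.1.1 already tabulates discontinuation reasons. If closure is coded as a reason of its own, the remaining reasons track true dropout to within about 4 points at 364 enrolled with accrual up to 12 months, and the defect shrinks to one missing code. This largely stands. It does not stand fully, because the SAP specifies no such code and the shortfall reaches about 6 points with 18-month accrual.

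It is also true that 364 is a ceiling, that the rule says approximately 100, and that with few enrolled the rule may never bind. The point is therefore conditional.

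Nor does tolerability rest on this table. The SAP also plans adverse events leading to discontinuation (Table 14.3.1.5), duration of exposure (14.1.5) and compliance (14.1.6), and neither document calls the completion percentage a tolerability measure. Those outputs do not estimate persistence, however. The first counts only stops attributed to adverse events, and exposure (SAP 7.3.1.4) runs to the end-of-treatment or withdrawal visit, so closure shortens it.

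Four stronger readings are tempting and are not supported:
- That women are scored only as completed or discontinued: reasons are tabulated as well.
- That completion must look poor: with completion undefined and an end-of-treatment visit required of everyone at closure, cut-off women could be coded either way.
- That comparisons across A01 groups are distorted: A01 was randomised, nothing suggests the groups entered at different calendar times, and the rule does not fix the split between them.
- That failing to reconsent is outside a woman's control: it is her own decision, so it counts as a stop.

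**Conclusion.** The point holds conditionally. If clearly more than 100 women would otherwise finish, overall completion is close to 100/N and nearly uninformative about persistence. At 364 enrolled, completion of 52 weeks of treatment is about 30% to 42% for true retention of 40% to 90%, with 6% to 60% of women stopped by the sponsor. The crude discontinuation percentage is a better guide if closure is separated out, but runs low by up to about 4 points with accrual of 12 months or less and about 6 points with 18 months.

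These sizes rest on assumed enrolment, uniform accrual and constant dropout. At 200 enrolled the problem appears only above about 50% retention.

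Kaplan-Meier removes the bias if entry date is unrelated to persistence. The change from 10 mg to 5 mg during the study means this is not guaranteed, and the curve would describe the mixed regimen as given.

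**What to change.** Before database lock, in SAP 8.1.1, Table 14.1.1 and its Ex4Site version:

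1. Define completion as 52 weeks of treatment.
2. Show *on treatment at sponsor closure* and *did not reconsent at dose change* as lines separate from the other discontinuation reasons.
3. Add a Kaplan-Meier estimate of persistence on study drug to 52 weeks after the first A02 dose, overall and descriptively by A01 group. The event is permanent stop of study drug, with non-reconsent counted as a stop. Censor only at sponsor closure or completion.
4. State how completers enter the 52-week estimate. The nominal end-of-treatment visit is 448 − 85 = 363 days after Visit 1, with a 7-day window (Protocol Table 1), so many would otherwise be censored just short of 364 days. Treating them as event-free to 52 weeks solves this.
5. Add a footnote that the raw completion percentage depends on the closure rule.

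The closure rule itself is unchanged. The cost is some SAP wording and one extra descriptive output. The protocol already records withdrawal dates and reasons (4.5.2) and treatment suspension dates and reasons (4.5.1), and the SAP already uses the first A02 dose date (7.3.1.4).

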#### **8.1.2 Demographic and Other Baseline Characteristics**

The subject demographic and baseline characteristic as below will be summarized by treatment group of MT-8554-A01, and overall in table and presented in data listing for the SAF population. (Table 14.1.2)

- Age (years)
- Sex
- Race
- Ethnicity
- Weight (kg)
- Height (cm)
- BMI (kg/m^2)
- Menopausal status
- Antidepressant use
- Diabetic status
- Cardiovascular history
- Hypertension
- Heart Failure
- Baseline labs (creatinine, the estimated glomerular filtration rate [eGFR], haematocrit)
- Average daily VMS frequency
- Average daily VMS severity

If any of the above demographic and baseline characteristic are not collected at week 12 then the data collected in study MT-8554-A01 baseline will be used.

#### **8.1.3 Medical History**

The medical and surgical history will be summarized by treatment group of MT-8554-A01, and overall, SOC and PT in table and presented in data listing for the SAF population. (Table 14.1.3).

The count and percentage of subjects who had at least one medical history or surgical history will be presented. For each medical history or surgical history term, the count and percentage of subjects will be presented.

#### **8.1.4 Concomitant Medications**

The concomitant medications will be summarized in table by treatment group of MT-8554-A01, and overall and presented in data listing for the SAF population (Table 14.1.4).

The count and percentage of subjects who had at least one concomitant medication will be presented. For each concomitant medication term, the count and percentage of subjects will be presented.

Concomitant medications are medications that started prior to, on or after date of first dose of study A02 medication and ended on or after date of first dose of study A02 medication. This includes medications deemed as ongoing at the end of study.

As part of concomitant medication, prohibited medication will be listed.

#### **8.1.5 Study Medication Exposure**

Duration of exposure to study medication in days will be summarized in table and presented in data listing for the SAF population. (Table 14.1.5)

#### **8.1.6 Treatment Compliance**

Compliance to study medication will be presented for the ITT population in table. (Table 14.1.6)

All study medication administration and accountability data will be listed by subject.

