7.2.1 Compliance

The prescribed dosage, timing and mode of administration of study medication may not be changed. Any departures from the intended dose regimen must be recorded in the eCRF.

Study medication accountability and subject compliance will be documented throughout the OLE period using study medication dispensing and return record logs.

Subjects will be asked to return all unused medication including empty and partially used bottles. Study medication dispensed at the previous visit will be collected by the site and compliance will be assessed by counting the returned drug.

Non-compliance is defined as taking [REDACTED] of study medication during any visit.

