**Table 2 Analysis populations**

Analysis Population	Definition
Safety(SAF) population	All subjects who receives at least 1 dose of study medication
Intent-to-treat (ITT) population	All subjects who have at least 1 post-baseline exploratory assessment

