### **7.3.1.5 Treatment Compliance**

Compliance with study medication—based on the drug accountability data—will be calculated as the number of days subjects take study medication divided by the duration of exposure in days, expressed as a percentage.

Study medication compliance will be calculated as follows:

$$\frac{\text{Cumulative Dosing days}}{(\text{date of end of treatment visit} - \text{date of first dose in A02})} \times 100\%$$

The subjects should take one dose daily per protocol.

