## 8.5 Exploratory Analysis Excluding Some Study Sites

During the MT-8554-A01, the Sponsor observed a significant degree of study drug non-compliance at a few study sites, where some of these were clustered geographically and had study subjects duplication.

The Sponsor also observed 8 study sites (site number 104, 108, 112, 114, 119, 128, 144, and 158) with significant IP non-compliance based on MT-8554 PK levels. Among them, 4 sites (site number 104, 112, 114, and 119) had highest number of IP non-compliance based on PK levels, were among the high enrollers (site number 112 and 114 were top enrollers and 104 and 119 were among the top 8 enrollers), and were located at a close proximity to each other in the South Florida. The Sponsor initiated a comprehensive re-review to verify the operational conduct of the study.

The Sponsor's review team concluded that at these 4 Florida sites, training and monitoring was conducted similar to all other sites as per standards, and no concerns were identified by the study monitors during the conduct of the study. The Sponsor considered the possibility that the subjects' poor IP compliance could be due to early onset adverse events which might have prevented them from continuation of MT-8554. However, it was noted that there was a lack of adverse events reporting from these 4 Florida sites in comparison to the all others sites. The incidences of AEs at these 4 sites were 31.8, 37.0, 31.6 and 4.3% as compared to 44.1, 39.7, 49.3 and 64.3% at the other sites in placebo, 1, 5, and 10 mg groups respectively, in MT-8554-A01.

Of these 4 sites, one site was identified a duplicate subject during the screening period, which was dropped out of the study. The Sponsor conducted an additional database search to exclude unidentified duplicate subjects. The Sponsor identified 12 subjects at these 4 Florida sites, which were suspected of being duplicates based on date of birth, height, weight medical history, and medications. Later, all these 12 subjects were confirmed by the quality assurance review of the sites as being duplicates, at least one subject at each site.

Therefore, it was considered to conduct the statistical analyses without the data from these sites. As the exploratory analyses, the main efficacy and safety analyses specified as following list will be performed with the ITT and safety population excluding the 4 sites subjects.

No.	Title of Table	Analysis Population

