14.1.1.Ex4Site	Subject Disposition and Analysis Population-Exclude 4 Florida site-	All Subjects
14.1.2.Ex4Site	Demography and Baseline Characteristics -Exclude 4 Florida site-	SAF
14.1.5.Ex4Site	Summary of Exposure to Study Medication: Duration of exposure -	SAF

No.	Title of Table	Analysis Population
	Exclude 4 Florida site-	
14.1.6.Ex4Site	Summary of Compliance to Study Medication-Exclude 4 Florida site-	SAF
14.2.1.Ex4Site	Summary of VMS Frequency-Exclude 4 Florida site-	ITT
14.2.2.Ex4Site	Summary of VMS Severity-Exclude 4 Florida site-	ITT
14.2.3.Ex4Site	Summary of Menopause Specific Quality of Life (MENQOL) Domain and Total Scores-Exclude 4 Florida site-	ITT
14.3.1.1.Ex4Site	Summary of Treatment Emergent Adverse Events (TEAE) -Exclude 4 Florida site-	SAF
14.3.1.1.A.Ex4Site	Summary of Treatment Emergent Adverse Events (TEAE) for before the dose change -Exclude 4 Florida site-	SAF
14.3.1.1.B.Ex4Site	Summary of Treatment Emergent Adverse Events (TEAE) for after the dose change -Exclude 4 Florida site-	SAF
14.3.1.2.Ex4Site	Incidence of Treatment Emergent Adverse Events by System Organ Class, Preferred Term-Exclude 4 Florida site-	SAF
14.3.1.2.A.Ex4Site	Incidence of Treatment Emergent Adverse Events by System Organ Class, Preferred Term for before the dose change-Exclude 4 Florida site-	SAF
14.3.1.2.B.Ex4Site	Incidence of Treatment Emergent Adverse Events by System Organ Class, Preferred Term for after the dose change-Exclude 4 Florida site-	SAF
14.3.6.1.Ex4Site	Transvaginal Ultrasound (TVU) -Exclude 4 Florida site-	SAF
14.3.6.2. Ex4Site	Transvaginal Ultrasound (TVU) - Endometrial Thickness-Exclude 4 Florida site-	SAF
14.3.7.1. Ex4Site	Endometrial Biopsy -Exclude 4 Florida site-	SAF

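### Compliance is tabulated on ITT for all sites but on the safety population when the four Florida sites are excluded, so the two tables differ by population as well as by site

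*SAP*

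**What the plan says.** **Population of the compliance tables.** SAP 8.1.6 states: "Compliance to study medication will be presented for the ITT population in table" (Table 14.1.6). The SAP 8.5 list includes "Summary of Compliance to Study Medication-Exclude 4 Florida site" (Table 14.1.6.Ex4Site) with SAF in its population column. The introduction to that list says only that the analyses "will be performed with the ITT and safety population excluding the 4 sites subjects", and gives no reason for moving compliance from one set to the other. Exposure is on SAF in both places (14.1.5 in SAP 8.1.5, and 14.1.5.Ex4Site in SAP 8.5).

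**Definitions.** SAP Table 2 defines SAF as "All subjects who receives at least 1 dose of study medication" and ITT as "All subjects who have at least 1 post-baseline exploratory assessment".

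**Protocol rule.** Protocol 10.2 assigns the Safety population to all analyses and summaries and ITT to clinical efficacy analyses. Protocol 10.3.1 repeats the Safety rule. Protocol 10.3.5 lists the efficacy endpoints as VMS frequency, VMS severity and MENQOL, so compliance is not among them. SAP section 10 records one change from the protocol, the baseline severity formula.

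**The compliance measure.** SAP 7.3.1.5 takes "the number of days subjects take study medication divided by the duration of exposure in days", which gives one percentage per woman for the whole of A02. Protocol 7.2.1 counts the returned drug at each visit and frames non-compliance by visit. The sentence opens "Non-compliance is defined as taking" and the threshold is redacted.

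**The concern.** SAP 8.5 exists because PK levels in A01 showed significant non-compliance at eight sites. Four of these, close together in South Florida, had the highest numbers. A reader will naturally compare compliance over all sites with compliance after those four are removed, to judge how far the A02 safety data come from women who took the drug. As planned, that comparison changes two things at once: the sites and the analysis set. A dosed woman with no post-baseline diary entry or MENQOL is left out of the all-sites table, but counts in the companion table if she attended one of the remaining sites.

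There is a lesser reporting point. A single whole-period percentage dilutes a long interruption, and no planned table counts the women who were non-compliant under the protocol's own per-visit definition.

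**Working it through.** The documents state no compliance figure to reproduce, so the check sets the tables side by side and then sizes the two effects.

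**1. Populations where a table's set is stated both in SAP 8.1 and in the SAP 8.5 list**

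| Table | SAP 8.1 | SAP 8.5 (four sites excluded) |
|---|---|---|
| 14.1.2 Demography | SAF | SAF |
| 14.1.5 Exposure | SAF | SAF |
| 14.1.6 Compliance | ITT | SAF |

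Of these, compliance is the only one that differs.

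**2. What the difference between the two compliance tables contains**

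(SAF without four sites) − (ITT all sites) = [(SAF without four sites) − (SAF all sites)] + [(SAF all sites) − (ITT all sites)]

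The first bracket is the site effect that the reader wants. The second is due to the population alone. Let s be the share of SAF outside ITT, c0 the mean compliance of that share, and c1 the ITT mean. Treating ITT as a subset of SAF, the second bracket is s × (c0 − c1). None of these three values is in the documents, so the range below is an assumption, with c1 = 95%:

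| s | SAF mean if c0 = 80% | SAF mean if c0 = 50% |
|---|---|---|
| 0% | 95.00 | 95.00 |
| 1% | 95 − 0.01 × 15 = 94.85 | 95 − 0.01 × 45 = 94.55 |
| 5% | 95 − 0.05 × 15 = 94.25 | 95 − 0.05 × 45 = 92.75 |
| 10% | 95 − 0.10 × 15 = 93.50 | 95 − 0.10 × 45 = 90.50 |

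The population term therefore runs from nil to 4.5 points over this assumed range. The subset assumption is itself not guaranteed, because the ITT definition states no dosing condition.

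**3. Dilution by the whole-period percentage**

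Inputs: nominal visit days 85, 141, 197, 281, 365 and 448 (SAP Table 1). Exposure under SAP 7.3.1.4 is 448 − 85 = 363 days. The intervals between visits are 56, 56, 84, 84 and 83 days. For one gap of g days with otherwise full dosing, whole-period compliance is (363 − g)/363. If the gap lies within one interval of length L, compliance in that interval is (L − g)/L.

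| Gap (days) | Whole period | 56-day interval | 84-day interval |
|---|---|---|---|
| 14 | 349/363 = 96.1% | 42/56 = 75.0% | 70/84 = 83.3% |
| 28 | 335/363 = 92.3% | 28/56 = 50.0% | 56/84 = 66.7% |
| 42 | 321/363 = 88.4% | 14/56 = 25.0% | 42/84 = 50.0% |
| 56 | 307/363 = 84.6% | 0/56 = 0% | 28/84 = 33.3% |

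The 42-day row is an illustration. It matches the 6-week limit for resuming treatment in protocol 4.5.1, which applies to clinically significant breast findings and unexplained uterine bleeding, not to routine dosing.

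**The case against.** The strongest reply is that the two sets will barely differ. One post-baseline assessment suffices for ITT, the VMS diary is daily from Visit 1, compliance calls are made at least every 4 weeks where there is no clinic visit, and MENQOL is scheduled at early termination. A dosed woman falls outside ITT only if she has neither a diary entry nor a MENQOL after baseline. Some such women may have no later visit at all. Under SAP 7.3.1.4, treatment for women lost to follow-up ends at the last visit, so their denominator could be about zero and compliance could not be computed in either set. Early stopping does not by itself lower the measure either, because the denominator stops at the withdrawal visit. All of this stands as an argument about size. It does not explain the switch or reconcile it with the protocol.

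Three stronger readings are tempting, and the documents do not support them:

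- **That the ITT choice narrows or reverses the gap between the tables.** If the omitted women complied poorly, the population term would work against any rise seen on removing the four sites. But nothing in the documents gives their number or their compliance, so neither narrowing nor reversal is established.
- **That long dosing gaps are hidden.** SAP 8.1.6 also plans a by-subject listing of all administration and accountability data. SAP 6.1 reports the minimum and maximum, SAP 7.3.1.4 subtracts missed days, and protocol 4.5.1 requires suspension dates and reasons in the eCRF. Gaps are diluted in the summary table but not lost from the report.
- **That correcting the table settles whether women took the drug.** The A01 problem was found through PK levels, whereas A02 compliance rests on drug accountability.

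It is also fair to say that protocol 7.2.1 does not promise a table by interval, and that its threshold cannot be read here. Interval rows are a reporting improvement and do not correct an error.

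**Conclusion.** The population mismatch is real, unexplained, and an undeclared departure from protocol 10.2 and 10.3.1. A difference between Tables 14.1.6 and 14.1.6.Ex4Site cannot be read as the effect of excluding the four sites alone. That conclusion rests on the stated table populations and needs no assumption. The size of the distortion cannot be determined from the documents and may be small or nil. The figures of up to 4.5 points depend wholly on assumed shares and compliance values.

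The dilution of gaps in the whole-period percentage is arithmetically clear (88.4% overall against 25.0% in the interval for a 42-day gap between Weeks 12 and 20, on nominal visit days). It supports an optional addition only.

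**What to change.** **Correction.** In SAP 8.1.6, present Table 14.1.6 on SAF. It then matches Tables 14.1.5 and 14.1.6.Ex4Site and the protocol rule, and the population term between the two compliance tables is zero by construction. This is a one-word change. The downside is a possibly slightly lower reported compliance figure. If ITT is kept on purpose, the sponsor should put both compliance tables on ITT and give the reason in SAP section 10.

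**Optional addition.** In both compliance tables, add compliance for each dispensing interval, and the count and percentage of women non-compliant at any visit under the sponsor's own protocol 7.2.1 threshold. The drug counts are already collected at visits, so the cost is programming a few extra rows in two tables. No new data or visits are needed.
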